13.2. Sample Size Determination

A total of 12 patients is planned to be randomized and exposed to trial product in this crossover trial on the basis of the following considerations.

The GIR results from 40 infants treated with IV glucagon for 24 hours published in the JIMD Research Report “The Effect of Continuous Intravenous Glucagon on Glucose Requirements in Infants with Congenital Hyperinsulinism.”¹⁴

“Overall there was a statistically significant reduction in the median (IQR) GIR during the 24h following initiation of continuous glucagon infusion compared to 24 h before initiation (18.5 (12.9, 22.8) to 11 (6.6, 17.5) mg/kg/min...”

This trial is powered to detect an effect in GIR for dasiglucagon after 48 hours compared to placebo of at least this effect size. Based on the longer infusion and titration of dasiglucagon in this trial, this is considered a conservative approach, allowing for some uncertainty when translating the published data into a clinical trial setting. Using unpublished individual patient data from the above-referenced study, the difference in GIR between the 2 treatment groups is assumed to follow a normal distribution. Assuming the true mean difference is 7.5 mg/kg/min with a standard deviation of differences of 7.36, the trial will have 89% power using a 1-sample t-test with 12 patients randomized to receive either placebo first and then dasiglucagon or vice versa.

13.3. Analysis Populations

Three analysis populations have been defined for this trial:

- The Safety Set: defined as all patients administered any randomized treatment.
- The Full Analysis Set (FAS): defined as all patients in the Safety Set who have a valid baseline efficacy assessment. Patients will be analyzed according to randomized treatment (Part 1) or overall patients (otherwise).
- Per protocol (PP) set: defined as all patients in the FAS without any major protocol deviations. Patients will be excluded from the PP set if they do not receive both treatments and/or do not have efficacy data available to evaluate the primary endpoint for both treatments.
- Pharmacokinetic Set (PK): defined as all patients in the Safety Set who have at least 1 measurement with quantifiable plasma concentration of dasiglucagon.

The primary analyses of the primary and key secondary endpoints will be based on the FAS. Supportive analyses of the primary and key secondary endpoints will be based on the PP. All safety analyses will be based upon the safety analysis set.

Inclusion in the analysis populations will be determined prior to database lock.

For the primary endpoint, baseline is defined as the IV GIR rate obtained at the end of the run-in period which corresponds to the last value obtained before randomization. During the 24-hour run-in period, all non-nutritional carbohydrates and carbohydrate fortification of feeds are prohibited as this might impact the GIR level and result in many updates during the run-in period. Therefore the IV GIR rate obtained at the end of the run-in period will give a better estimate of the stabilized value of GIR. For the second period of the crossover (Part 1), the IV GIR is also started at the IV GIR obtained at the end of the run-in period. For the purpose of all other efficacy analyses where applicable, baseline is defined as the last measurement prior to the start of trial drug administration on Day 1.

13.4. Statistical Analyses

This section presents a summary of the planned statistical analyses. A statistical analysis plan (SAP) that describes the details of the analyses to be conducted will be finalized prior to database lock.

Unless otherwise indicated, testing of statistical significance will be 2 sided with a significance level of $\alpha = 0.05$.

Continuous endpoints will be summarized with number (n), mean, standard deviation (SD), median, minimum, and maximum. In addition, change from baseline values will be calculated at each time point and summarized descriptively; the exception to this is the time of PG within prespecified ranges, which will not have a baseline value. For categorical endpoints, descriptive summaries will include counts and percentages.

All data will be presented in the data listings.

Immunogenicity data will be analyzed descriptively. No statistical tests are planned. Baseline ADA-positive patients will be calculated as a percentage of the total number of patients whose baseline samples were tested for ADA. Overall ADA incidence, the combined results of treatment-induced and treatment-boosted ADA-positive patients will be calculated as a percentage of the total number of evaluable patients, excluding baseline positive patients without

any samples available after drug administration. Titers will be reported as median and interquartile range.

Graphical presentations of selected endpoints will be prepared and will be outlined in the SAP.

13.4.1. Trial Patients and Demographics

13.4.1.1. Disposition and Withdrawals

The numbers of patients randomized, completing, and withdrawing, along with reasons for withdrawal, will be tabulated overall and by treatment sequence. The number of patients in each analysis population will be reported.

13.4.1.2. Protocol Deviations

Protocol deviations will be provided in a listing and summarized if appropriate.

13.4.1.3. Demographics and Other Baseline Characteristics

Demographic and baseline characteristics (including age, sex, race, ethnicity, weight, and length) at screening will be summarized using descriptive statistics. No formal statistical analyses will be performed.

Prior and concomitant medications and procedures will be summarized by treatment sequence (prior medications and procedures) or treatment and part (concomitant medications and procedures), by the number and percentage of patients taking each medication, classified using World Health Organization Drug Dictionary Anatomical Therapeutic Chemical classes and preferred term (PT).

13.4.2. Duration of Exposure and Compliance

Trial drug administration (i.e., amount administered) will be summarized in terms of each patient's mean, mode, and final dose, and in terms of duration of exposure. Descriptive statistics for these quantities, including the mean, median, SD, minimum, maximum, and quartiles, will be provided by treatment and part.

13.4.3. Efficacy Analyses

13.4.3.1. Primary Analysis

The mean IV GIR in the last 12 hours of each treatment period during Part 1 will be analyzed for the FAS and PP populations. The hypothesis:

$$H_{11}: \text{Reduction in weighted mean IV GIR}_{\text{dasiglucagon}} = \text{Reduction in weighted mean IV GIR}_{\text{placebo}}$$

will be based the last 12 hours of each treatment period, calculated as a weighted mean across the 12 hours, taking the actual time periods between the measurements into account (corresponding to calculating the area under the curve [AUC] and dividing by the length of the time period, i.e., weighted mean IV GIR). The IV GIR endpoint is expressed as glucose in mg/kg/min, i.e., data reported from different concentrations of the glucose used for infusion will be transformed to this standardized unit prior to analysis.

The primary analysis is defined by the estimand based on the treatment policy (de-facto) strategy, where the actual GIR measurement reported irrespective of adherence to treatment or

use of subsequent therapy is used. The reduction in weighted mean IV GIR between placebo and dasiglucagon will be estimated.

The weighted mean IV GIR will be analyzed using a mixed-model regression approach, with treatment and period as fixed effects and patient as a random effect. The 2-sided 95% confidence interval (CI) for the treatment difference will be calculated from the mixed regression model.

Missing data will be imputed using the following methodology: if the weighted mean IV GIR is missing for the placebo period, it will be imputed using the baseline weighted mean IV GIR; if the weighted mean IV GIR is missing for the dasiglucagon period, it will be imputed using the placebo-weighted mean IV GIR for that patient. As a sensitivity analysis, the primary endpoint will be re-analyzed as follows: 1) using only complete cases (i.e., weighted mean IV GIR is non-missing for both placebo and dasiglucagon) and 2) imputing missing weighted mean IV GIR using the baseline weighted mean IV GIR and 3) imputing missing dasiglucagon values during one period with the placebo value for that patient and imputing missing placebo values with the mean values of placebo patients for that period.

13.4.3.2. Key Secondary Analyses

The hypothesis:

$$H_{12}: \text{Total amount (g) of carbohydrates administered (regardless of the route) per day dasiglucagon} = \text{total amount (g) of carbohydrates administered (regardless of the route) per day placebo}$$

between the 2 treatment groups will be analyzed by using a mixed-model regression approach, with treatment and period as fixed effects and patient as a random effect. The total amount (g) of carbohydrates administered (regardless of the route) per day is the sum of the last 48 hours of each period in Part 1.

For the key secondary endpoint, 2-sided 95% CIs for the treatment differences will be estimated from the mixed-model. Missing dasiglucagon values during one period will be imputed with the placebo value for that patient and missing placebo values will be imputed with the mean values of placebo patients for that period. In addition, a sensitivity analysis will be performed using complete cases.

13.4.3.3. Secondary and Other Efficacy Analyses

Part 1

A mixed-model regression approach will be used to analyze the weighted mean IV GIR over 48-hour treatment period during Part 1 (dasiglucagon or placebo administration) similar to the primary analysis for the primary endpoint.

A generalized estimating equation (GEE) method with a logit link function will be used to analyze the weighted mean IV GIR below 10 mg/kg/min in the last 12 hours of each treatment period during Part 1 (yes/no) (dasiglucagon or placebo administration) to account for repeated observations in patients. In case of non-convergence, a Mc Nemar test will be used.

No sensitivity analysis will be used on these endpoints.

Part 2

Due to the potential impact of pancreatectomy on the secondary endpoints during Part 2, any endpoint assessment after pancreatectomy will not be included in the primary analyses

(endpoints set to missing after pancreatectomy). Sensitivity analyses will be run on those endpoints including all assessments in the descriptive analyses.

For Part 2 efficacy endpoints, continuous and categorical endpoints will be presented using summary statistics or frequencies, respectively; no formal testing will be performed. For the time to complete weaning off IV GIR, the time to actual hospital discharge and the time to pancreatic surgery, Kaplan-Meier curves will be produced.

13.4.4. Safety and Tolerability Analyses

Safety analyses will be conducted using data from the Safety Population (as defined in Section 13.3). Safety assessments will include the evaluation of AEs; clinical laboratory assessments (hematology, biochemistry, and ADAs); vital signs, physical examinations; ECGs, echocardiography, and local tolerability issues. No formal inferential analyses will be conducted for safety variables, unless otherwise noted.

Baseline is defined as the last nonmissing assessment before the first exposure to trial drug in the trial.

All safety analyses will be summarized by treatment received within treatment period and part and by trial visit, if applicable.

13.4.4.1. Adverse Events

Adverse events will be coded using the most current version of MedDRA.

A treatment-emergent AE is defined as an AE with an onset at the time of or following the start of treatment with the trial drug through the Follow-up Visit or Early Termination Visit, whichever occurs first.

The number and percentage of patients with AEs, as well as the number of AEs, will be displayed by system organ class, PT, and treatment group. The incidence of AEs will also be presented by severity and relationship to the trial drug. Serious AEs, AESIs and AEs resulting in discontinuation of trial drug will be summarized separately in a similar manner. Patient listings of AEs, SAEs, AESIs, and AEs causing discontinuation of trial drug and withdrawal from the trial will be produced.

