
	
Key Secondary Endpoints
 
Part 1, Day 1 to 4
 
The key secondary endpoint of total amount of gastric carbohydrates administered will be analyzed by using a mixed-model regression approach, with treatment and period as fixed effects and patient as a random effect.
 
Safety Analyses
 
Adverse events will be coded using the latest version of the Medical Dictionary for Regulatory Activities (MedDRA). Adverse events that begin after the first dose of trial drug will be defined as treatment emergent. The overall incidence of AEs will be displayed by system organ class, preferred term, and treatment. The incidence of AEs will also be presented by severity and by relationship to the trial drug. Vital signs, clinical laboratory measures (including hematology, biochemistry, and incidence of anti-drug antibodies [ADAs]), 12-lead electrocardiograms (ECGs), echocardiography, physical examinations, and local tolerability data will be summarized by treatment, where applicable. Out-of-range safety endpoints may be categorized as low or high, where applicable.
 
Safety results will be summarized by treatment received within treatment period and part and by trial visit, if applicable.
 
A formal statistical analysis plan (SAP) will be prepared to provide further details on the methods for statistical analysis.
 
No interim analysis is planned.

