9.3. Premature Patient Withdrawal

Randomization day exclusion criteria are described in Section 9.2.3.

Patients' parent(s)/guardian will be advised that they are free to withdraw their child from participation in this trial at any time, for any reason, and without prejudice. Every reasonable attempt should be made by the investigator to keep patients in the trial to obtain data for the primary endpoint in Part 1 and for safety follow-up even if trial treatment has been discontinued. However, patients must be withdrawn from the trial if their parent(s)/guardian withdraw consent to participate.

Investigators must attempt to contact patients' parent(s)/guardian who fail to attend scheduled visits by telephone or other means to exclude the possibility of an AE being the cause of withdrawal. Attempts to contact the patient must be documented. At least 3 phone calls and 3 written attempts to contact the patient will be made prior to considering them lost to follow-up. Should an AE be the cause of withdrawal, it must be documented, reported, and followed up as described in Section 12.3.

If a patient/parent(s)/guardian withdraws consent, the reason for withdrawal and the date of withdrawal will be recorded on the appropriate page of the electronic case report form (eCRF). Whenever possible and reasonable, the evaluations that were to be conducted at the completion of the trial should be performed at the time of premature withdrawal.

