9.4. Treatment Discontinuation

To prevent missing data, patients should, to the extent possible, be kept in the trial; therefore, treatment discontinuation is often the preferred option in case of, e.g., substantial noncompliance with trial procedures or initiation of prohibited treatment that interferes with the efficacy and safety evaluation. If it is an investigator's decision to discontinue the patient's treatment, the investigator should, whenever possible, discuss the potential discontinuation of the treatment with the medical monitor. If the patient is discontinued from trial treatment by the investigator or by parent/guardian's decision, the reason for treatment discontinuation and the date of treatment discontinuation will be recorded on the appropriate page of the eCRF. The patient should be asked to continue in the trial by following the planned visit schedule and to have trial assessments performed according to the Schedule of Events. This is especially important during Part 1 of the trial where the primary endpoint is evaluated. As a minimum, the patient will be asked to attend the Follow-up Visit 28 days (\pm 3 days) after discontinuation of trial treatment.

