12.2. Collection, Recording, and Reporting of Adverse Events

All AEs, whether serious or nonserious, will be reported from the time a signed and dated ICF is obtained until the end of the posttreatment follow-up period (which may include contacts for follow-up of safety) or inclusion in the ZP4207-17106 trial. Parent(s)/guardian will be asked about their child's condition by open questioning, such as "How has your child been feeling since you were last asked?" at each contact with the trial site (visit or telephone).

Parent(s)/guardian will also be encouraged to spontaneously report AEs occurring at any other time during the trial. In addition, patients will be observed for any signs or symptoms.

All AEs, regardless of seriousness, severity, or presumed relationship to the trial drug, must be recorded and evaluated by the investigator. Whenever possible, diagnoses should be given when signs and symptoms are due to a common etiology. If no diagnosis can be made, the investigator should record each sign and symptom as individual AEs. Investigators must record their opinion concerning the relationship of the AE to the trial drug. All measures required for AE management must be recorded in the source document and reported according to sponsor instructions.

Each AE must be reported on the AE eCRF within 5 days of the investigator becoming aware of the event.

All AE information should at a minimum include the following:

- Date and time of onset
- Date and time of investigator's first information about the AE
- Seriousness
- Severity
- Causal relationship with trial product
- Measures taken due to AE
- Interruption or discontinuation of treatment with trial product
- Date and time of resolution and final outcome

Each AE will be coded using the latest version of the Medical Dictionary for Regulatory Activities (MedDRA).

All SAEs, including those spontaneously reported to the investigator within 30 days after the last dose of trial drug, must be reported within 24 hours after obtaining knowledge about the event by

completing the SAE form in the EDC system. A separate SAE form should be completed for each SAE.

All SAEs will be reported in EDC; for each reported event a system-generated e-mail will be sent to the safety CRO (████████), medical monitor, sponsor medical director, and trial manager.

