14.6.2. Premature Trial Termination

The trial may be terminated prematurely for any reason and at any time by the sponsor, the IRBs/IECs, regulatory authorities, respective steering committees, or the coordinating investigator. A decision to terminate the trial prematurely is binding to all investigators at all trial sites.

Within 15 days of premature termination of a clinical trial, the sponsor or its designee and/or site will notify the IRBs/IECs and regulatory authorities on the premature termination as required according to national laws and regulations. The sponsor or its designee must clearly explain the reasons for premature termination.

If the trial is terminated prematurely, all investigators must inform their patients and take care of their appropriate follow-up and further treatment to ensure protection of their interests. Trial sites may be asked to have all patients currently participating in the trial complete all of the assessments for an Early Termination Visit.

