9.1.2. Deaths and Serious Adverse Events

Any deaths that occur during the study will be listed.

Serious TEAEs and Related Serious TEAEs will be listed and also tabulated by SOC and PT and presented by part and treatment group and overall for Dasiglucagon group.

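### The treatment-emergent window closes at an Early Termination Visit if that comes first, so a child who leaves the trial that way can have a reportable SAE within 30 days of last dose that the SAP's SAE tables omit

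*Protocol*

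**What the plan says.** **Window.** Protocol 13.4.4.1, in both the German and the non-German version, treats an event as treatment-emergent if it starts at or after the first dose and "through the Follow-up Visit or Early Termination Visit, whichever occurs first". SAP 6.1.7 and 9.1 use the same rule. The protocol synopsis differs: "Adverse events that begin after the first dose of trial drug will be defined as treatment emergent". It gives no end to the window.

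**Collection.** Under Protocol 12.2, adverse events in general are collected from consent "until the end of the posttreatment follow-up period" or until inclusion in the extension trial. The 24-hour reporting duty covers "All SAEs, including those spontaneously reported to the investigator within 30 days after the last dose of trial drug".

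**Leaving early.** The protocol separates two situations.
- A child who stops trial drug is asked to stay in the trial and follow the visit schedule (Protocol 9.4): "As a minimum, the patient will be asked to attend the Follow-up Visit 28 days" (± 3 days) after stopping.
- For a child who leaves the trial, Protocol 9.3 says the end-of-trial evaluations, where feasible, "should be performed at the time of premature withdrawal". It does not call this an Early Termination Visit.

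Apart from the treatment-emergent definition, that visit is named only in Protocol 14.6.2, for termination of the whole trial, where sites may be asked to have current patients "complete all of the assessments for an Early Termination Visit". The Schedule of Events has no column for it.

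**Reporting.** SAP 9.1.2 says "Serious TEAEs and Related Serious TEAEs will be listed and also tabulated by SOC and PT". The tables in SAP 9.1, 9.1.1 and 9.1.3 are also limited to treatment-emergent events. SAP 6.1.8 puts all collected data in listings, and SAP 9.1.2 lists deaths during the study without that limit.

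**The concern.** The end of the window depends on which visit a child happens to have, while SAE reporting runs on time since last dose. The two clocks can separate. Where they do, an SAE that the site must report is not treatment-emergent, and the SAP has no table for SAEs outside the window.

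The length of post-dose follow-up in the tables then depends on how a child left the trial. The cut-off can only remove events from the tables, never add them. The visit that can close the window earliest has no stated timing. With 12 children planned and withdrawals not replaced (Protocol 8.3 and 9.6), a single omitted event is visible in an incidence table.

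**Working it through.** **Inputs**
- SAE reporting limit: 30 days after last dose (Protocol 12.2).
- Follow-up Visit: 28 days after last dose (Protocol 11.1), ± 3 days (Schedule of Events; Protocol 9.4 for a child who stops treatment).
- Early Termination Visit: no timing given, so it is varied below as an assumption.
- Planned number: 12 children.

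**The plan's own calendar.** Screening 28 + Part 1 4 + Part 2 21 + follow-up 28 = 81 days, the stated maximum duration. Follow-up falls on Day 25 + 28 = Day 53, as scheduled. The calendar is consistent.

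**Days of the 30-day SAE period outside the window.** If the visit that closes the window takes place x days after last dose, the gap is max(0, 30 − x).

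| Closing visit | x | Gap (days) |
|---|---|---|
| Follow-up, early limit | 25 | 5 |
| Follow-up, nominal | 28 | 2 |
| Follow-up, late limit | 31 | 0 |
| Early Termination (assumed) | 0 | 30 |
| Early Termination (assumed) | 7 | 23 |
| Early Termination (assumed) | 14 | 16 |
| Early Termination (assumed) | 28 | 2 |

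**Which child meets which row.** A completer who does not enter the extension, or a child who stops drug and attends Follow-up at 28 ± 3 days, is in the first three rows: 0 to 5 days. Only a child with an Early Termination Visit is in the last four.

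**Effect of one omitted SAE.** 1/12 = 8.3 percentage points on SAE incidence, provided that child has no other SAE in the same table. If the child has one, the incidence does not move.

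**The definitions side by side.** Take an SAE ten days after last dose in a child whose Early Termination Visit was on the day of last dose. It is reportable under Protocol 12.2 and treatment-emergent under the synopsis. It is not treatment-emergent under Protocol 13.4.4.1 or the SAP, so it is absent from the SAP's SAE tables and present in the listings.

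**Extension entrants.** The Follow-up Visit is only for children who do not enter the extension (Schedule of Events, footnote a). For entrants the Section 13 window has no stated end, although collection stops at inclusion in the extension trial.

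**The case against.** A reader might infer that any child who stops treatment early loses the post-treatment period from the tables. The documents do not support that. Protocol 9.4 keeps such a child in the trial and asks for a Follow-up Visit at 28 ± 3 days as a minimum, which leaves at most 5 days outside.

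The large gap rests on two readings. One is that the withdrawal assessments in Protocol 9.3 count as an Early Termination Visit, which is plausible but not stated. The other is that the visit falls at or near last dose, which is assumed. What is certain is that the window refers to a visit with no schedule.

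It would also be too strong to say that SAEs are actively collected for 30 days after a child leaves. Protocol 12.2 covers spontaneous reports, and no contact up to day 30 after a withdrawal visit is described.

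Nor are the events hidden. They stay in the listings, deaths are listed regardless of the window, and the protocol's own sentence on summarizing SAEs is not expressly limited to treatment-emergent ones. All of this stands and reduces the importance of the point. It does not remove the mismatch, because SAE incidence is read from the SAP's tables.

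A further objection concerns the remedy. A flat limit of 30 days after last dose could shorten the window for some children. One who stops on Day 3 and follows the planned schedule to Day 53 now has 53 − 3 = 50 days counted; a flat limit would drop 20 of them. That objection is right, and the fix below allows for it.

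**Conclusion.** The point holds in a limited form. Under Protocol 13.4.4.1 and the SAP, a child who leaves the trial with an Early Termination Visit can have a reportable SAE that the SAP's SAE tables leave out. Up to 30 of the 30 days are outside if that visit is on the day of last dose, a timing that is assumed. For a child who only stops treatment and attends Follow-up at 28 ± 3 days, the gap is 0 to 5 days. The synopsis gives a different definition, so the text needs reconciling in any case.

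It is tempting to go on and say that the safety tables are biased towards a better profile. The direction of any omission is clear, but the documents give neither an expected number of affected children nor evidence that early leavers have more SAEs, so no size of bias can be claimed.

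Severity is minor. Safety analysis is descriptive, 12 children are planned, and Protocol 20.4.3 (German version) expects few drop-outs. The shift of 8.3 points applies only where the omitted SAE is the child's only one in the table.

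**What to change.** Use one definition in the synopsis, Protocol 13.4.4.1, and SAP 6.1.7 and 9.1: onset from first dose through the later of (a) the last trial visit, whether Follow-up or Early Termination, and (b) 30 days after the last dose of trial drug, or until entry into the extension trial if that is earlier.

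With this rule the gap in the table above is 0 in every row, a Follow-up Visit on day 31 loses nothing, and the child who stops on Day 3 keeps all 50 days. It also gives extension entrants a stated end to the window.

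State alongside it that, after an Early Termination Visit, the added days rest on spontaneously reported SAEs. Non-serious events will be less completely captured there, and the tables should not be read as if follow-up were equal.

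The cost is a short text change in several places: the synopsis and 13.4.4.1 in two protocol versions (2 × 2 = 4) plus two SAP sections, so 6 in all. The protocol part needs an amendment under Protocol 14.8. No new data collection is required. A few more events may appear in the tables.
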